#### **9.1 Analysis sets**

The screened set (SCR) will include all patients who provided informed consent.

The full analysis set (FAS) will include all randomized patients who received at least one dose of study drug. It was considered reasonable to limit the FAS to patients who took trial medication, because the decision on whether or not study drug is started will not be influenced by the treatment group assignment due to the effective treatment blinding procedures described in [Section 5.4](#). Following the intent-to-treat principle, patients will be analyzed according to the treatment they were assigned to at randomization.

The per-protocol set (PPS) will include all patients in the FAS without any major protocol deviations such as violation of major entry criteria or low compliance. Patients may also be considered censored for the PPS analysis at the time of major post-baseline protocol deviations. Major protocol deviations will be defined in the study specification document

prior to database lock and the un-blinding of the study. Patients will be analyzed according to the treatment they received.

The safety set (SAF) will include all patients who received at least one dose of double-blind study drug. Patients will be analyzed according to the treatment they received.

The analysis of the primary objective will be performed on the FAS. The PPS will be used for the supportive analysis of the primary and the secondary variables. The FAS will be used for the analysis of all other efficacy variables. The SAF will be used in the analysis of all safety variables.

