2.2 Analysis sets

The following analysis sets are defined:

- The screened set (SCR) will include all patients who provided informed consent.
- The randomized (RAN) set will consist of all patients who were assigned a randomization number, regardless of whether or not they actually received study medication. Patients in RAN will be analyzed according to the treatment they were randomized to.
- The Full Analysis Set (FAS) will consist of all randomized patients who received at least one dose of study medication. It was considered reasonable to limit the FAS to patients who took trial medication, because the decision on whether or not study drug is started will not be influenced by the treatment group assignment due to the effective treatment blinding procedures. Following the intent-to-treat principle, patients will be analyzed according to the treatment they were assigned to at randomization. The FAS will be used for the analysis of all efficacy endpoints, and for the summaries of patient disposition, demographic and baseline characteristics.
- The Per-Protocol Set (PPS) will include all patients in the FAS who did not have any major protocol deviations such as violation of major entry criteria. Protocol deviations will be defined in the data review plan document prior to database lock and the un-blinding of the study. Protocol deviations leading to exclusion from analysis sets are

defined in Section 6.7. Patients in the PPS will be analyzed according to the treatment they actually received. The PPS may be used for supportive analysis of the primary efficacy endpoint.

- The Safety Set (SAF) will consist of all patients who received at least one dose of double-blind study drug. Patients will be analyzed according to the treatment they received. The SAF will be used in the analysis of all safety variables. If due to a dispensing error a patient erroneously received any study treatment which is different from the randomized treatment, the patient will be analyzed according to the treatment they were randomized to.

Note that the set of patients included in the FAS and SAF are the same except that the SAF allows the inclusion of non-randomized patients who receive study drug in error.

In cases where an incorrect randomization stratum is entered in the IRT (interactive response technology), the corrected stratum information as per the CRF data will be used for reporting and analysis.

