2.4 Treatments (study treatment, rescue medication, concomitant therapies, compliance)

2.4.1 Study treatment / compliance

2.4.1.1 Duration of exposure

Duration of exposure to a treatment will be calculated as the number of days between the first dose date and the last dose date exposed to that treatment over the specified period (expressed as: Duration of exposure = Date of last known dose of study drug – Date of first dose of study drug + 1).

The duration of exposure will be summarized by treatment group for the safety set as a continuous variable with the standard descriptive statistics.

The number of patients who completed the 12-week study treatment and who discontinued prematurely will be shown including the reasons for discontinuation of study treatment. In addition, the duration of exposure will be summarized as a categorical variable classified into <4 weeks, >=4 to <12 weeks, >=12 weeks.

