Note: death refers to adverse events with fatal outcome on-study.

Within category 1, patients with higher change from baseline FEV₁ at Week 12 will be ranked greater than patients with lower change from baseline. Patients who completed the trial with missing FEV₁ data at Week 12 will be ranked lower than anyone who completed the trial with non-missing FEV₁ data at Week 12. Within that, patients with higher change from baseline in FEV₁ at a later visit will get higher ranks. In case of ties in the visits with last available FEV₁ data, patients with higher change from baseline in FEV₁ are assigned a higher rank. In case of ties in the FEV₁ values, midranks will be used.

Within categories 2 and 3, patients that withdraw from the trial later will get higher ranks than patients that withdraw early. In cases in which patients withdraw at same study day, patients with higher change from baseline in FEV₁ at a later visit will get higher ranks. In case of ties in the FEV₁ values or no available post-baseline assessments of the primary variable, midranks will be used.

A Wilcoxon rank-sum test (Van Elteren test) stratified by age group (<18 vs. ≥18 years), use or non-use of a second asthma controller medication, and region will be used to analyze the ranked data.

Per-protocol analysis

The primary analysis may be repeated for the PPS.

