2.7 Safety analyses

All safety evaluation will be based on the safety analysis set.

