- Section 9.2 in the study protocol states that the age of the patient will be calculated from the date of birth to date of Visit 1. However, since date of birth is not captured on the CRF page and age (in years) at the time of informed consent is entered into CRF, there is no need to re-calculate age.
- Shift tables relative to the normal reference ranges to summarize the on-treatment change from baseline to post-baseline for each laboratory parameter or ECG parameter or vital sign assessments will not be presented.
- Study protocol defines treatment emergent adverse events as those events starting on or after the time of the first intake of study drug and until the day after the last intake of study drug. However, in order to maintain consistency with the submission documents, for analysis purposes the following updated definitions are considered:
AEs starting on or after the time of the first intake of study drug and not later than 7 days (30 days in the case of a serious AE) after the last intake of study drug will be classified as a TEAE.
- Added the responder analysis for AQLQ improvement
- Added more details to liver function tests including eDISH plot
- Added analysis for renal events and liver events according to project level alignment
- The following analyses, though pre-specified in the protocol, may not be critical for decision making purposes and hence will be reported outside of CSR:

- 

- In protocol 9.4.4, supportive analysis for the primary endpoint based on other missing data imputation approaches: pattern mixture approach combining the jump to reference and missing at random approaches by distinguishing reasons for discontinuation of treatment and retrieved dropout imputation approach.
- In protocol Section 9.4.4, subgroup analyses for BMI, number of exacerbations in the previous year, ACQ tertiles, [REDACTED].
- Summaries on post-treatment discontinuation events to be produced for adverse events and serious adverse events by system organ class and preferred term.

6 Appendix

This appendix gives details about statistical methods in addition to the report text. All analyses will be performed by using SAS Version 9.4.

Note: The SAS version that will be actual on the NOVARTIS platform at the time when the study is completed will be stated here.

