6.7 Rule of exclusion criteria of analysis sets

Subject classification in the analysis sets (FAS, Safety, Per Protocol, SCR, and RAN) will be based on protocol deviation specifications and non-protocol deviation classification criteria as following.

Table 6-7-1 Protocol deviations that cause subjects to be excluded

Deviation ID	Description of Deviation	Exclusion in Analyses
INCL01a	Informed consent was not obtained	SCR, RAN, FAS, PPS, SAF
INCL02	Age < 12 years	PPS
INCL03	No current diagnosis of Asthma of at least 6 months prior to V1	PPS
INCL05a	For patients aged >= 18 years, % predicted FEV1 was not <= 85% at both V1 & V101	PPS
INCL05b	For patients aged 12 years to <18 years, % predicted FEV1 was not <= 90% at V1 & V101	PPS
INCL05c	Spirometry done for assessing study eligibility is not meeting ATS/ERS criteria for acceptability or repeatability.	PPS
INCL08	Reversibility not demonstrated before randomization	PPS
EXCL01	Other investigational drug used within 30 days or within 5 half-lives prior to Screening	PPS
EXCL10b	Smoking history of greater than 10 pack years	PPS
EXCL11	Patient had an asthma exacerbation requiring systemic corticosteroids, hospitalization, or emergency room visit within 6 weeks prior to Visit 1	PPS

Deviation ID	Description of Deviation	Exclusion in Analyses
EXCL12	Patient had an asthma exacerbation requiring systemic corticosteroids, hospitalization or emergency room visit during the screening or placebo run-in periods.	PPS
EXCL13	Patients had respiratory tract Infection or asthma worsening within 4 weeks prior to V1.	PPS
COMD01	Prohibited asthma related ConMed during treatment epoch	PPS
COMD04	Permitted asthma related medication not taken as allowed under certain conditions during treatment epoch	PPS
COMD05	Baseline asthma medication or their dose was changed after Visit 1	PPS
OTH04	Patient randomized in error	PPS

Table 6-7-2 Subject Classification

Analysis Set	PD ID that cause subjects to be excluded	Non-PD criteria that cause subjects to be excluded
SCR	INCL01a,	NA
RAN	INCL01a	NA
FAS	INCL01a	Not in RAN; Randomized and no double-blind study drug taken
PPS	INCL01a,INCL02,INCL03, INCL05a,INCL05b,INCL05c, INCL08,EXCL01,EXCL10b, EXCL11,EXCL12, EXCL13,COMD01,COMD04 ,COMD05,OTH04	Not in FAS;
SAF	INCL01a	No double-blind study drug taken

7 Reference

[name] (2004). Asthma Control Questionnaire: Background, Administration and Analysis

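### The SAP's dispensing-error exception would tabulate a patient who took only the other arm's drug under a treatment not taken in the double-blind period, contrary to the protocol's as-treated Safety Set

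*SAP*

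**What the plan says.** Protocol 9.1 admits to the Safety Set everyone with at least one "dose of double-blind study drug. Patients will be analyzed according to the treatment they received". It makes no exception.

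SAP Section 1 commits to analysing the data as protocol Section 9 sets out. The Safety Set bullet in SAP 2.2 repeats the as-treated rule and then adds one for dispensing errors. A patient given, by such an error, any study drug "which is different from the randomized treatment, the patient will be analyzed according to the treatment they were randomized to". No minimum or maximum amount, duration or share of exposure is attached.

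The set is used widely. SAP 2.7 states: "All safety evaluation will be based on the safety analysis set". SAP 2.4.1.1 adds: "The duration of exposure will be summarized by treatment group for the safety set as a continuous variable with the standard descriptive statistics".

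SAP Section 4 lists changes from the protocol. One concerns safety and begins "Study protocol defines treatment emergent adverse events as those events starting on or after"; it widens the window for treatment-emergent events. No readable entry mentions how Safety Set patients are assigned to arms.

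For the Per-Protocol Set, SAP 2.2 says: "Patients in the PPS will be analyzed according to the treatment they actually received". That set has no dispensing-error exception.

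**The concern.** An as-treated safety population exists so that harms are attributed to the drug the patient took. In this trial treatment is blinded and kits are allocated by IRT. A dispensing error is therefore the main way in which a randomised patient's received drug can differ from the assigned one. The SAP's exception removes that situation from the as-treated rule.

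The clear failure is the patient who took only the other arm's drug. An event on QAW039 in a patient randomised to placebo would be tabulated under placebo, or the reverse. Exposure would be credited to the wrong arm too. The plan looks for infrequent harms: protocol 7.7 monitors idiosyncratic reactions, and the SAP tabulates Hy's law cases and plots eDISH. In such displays the arm in which a single case appears can change how it is read.

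A secondary inconsistency follows. SAP Table 6-7-1 ("Protocol deviations that cause subjects to be excluded") contains no wrong-drug deviation. A misdispensed patient could therefore sit in one arm in the safety tables and in the other in the per-protocol efficacy analysis.

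**Working it through.** The plan gives no figure to reproduce on this point. The check is a comparison of rules, followed by an illustration of size.

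**1. Rules side by side, for randomised patients**

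| Patient | Protocol 9.1 | SAP 2.2, Safety Set |
|---|---|---|
| Took only the randomised drug | that drug | same |
| Took both drugs through a dispensing error | no rule stated | as randomised |
| Took only the other arm's drug through a dispensing error | drug taken | as randomised |

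The second row fills a gap in the protocol. The third row contradicts it. Non-randomised patients given drug in error, whom SAP 2.2 also admits, have no randomised arm, so the exception cannot apply to them.

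**2. Is it declared?** The readable items in SAP Section 4 cover age derivation, shift tables, the treatment-emergent window, the AQLQ responder analysis, liver and renal additions, and analyses moved outside the study report. None concerns the Safety Set. One bullet is blank, but it falls under analyses moved outside the report, which is not where a change to an analysis set would be expected.

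**3. One misplaced event.** Input: 325 per arm (protocol 9.8). Suppose a patient randomised to placebo took only QAW039 and had the only event of its kind. The difference is QAW039 minus placebo.

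- As randomised: 0/325 − 1/325 = −0.308 percentage points.
- As treated (326 and 324 patients): 1/326 − 0/324 = +0.307 points.
- Shift: 0.308 + 0.307 = about 0.61 points, with the sign reversed.

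**4. Common events.** Assume m patients fully crossed in each direction and true rates of 4% and 1%. These values are illustrative. The tabulated difference is (4% − 1%) × (1 − 2m/325).

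- m = 1: 3.00 × (1 − 2/325) = 2.98 points.
- m = 10: 3.00 × (1 − 20/325) = 2.82 points.

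**5. How many patients?** The documents give no error rate. Assume independent errors, with the other arm's drug handed out at 0.1% to 2% of dispensing visits. A completer would need an error at all four dispensing visits (weeks 0, 2, 4 and 8): 650 × 0.02⁴ = 0.0001 patients at the top of the range. The likelier route is a wrong first supply followed by an early stop. The protocol assumes 15% discontinue treatment, which is 650 × 0.15 = 97.5 patients. If all of them stopped before the second supply, 97.5 × 0.001 to 97.5 × 0.02 = 0.1 to 2 patients would have taken only the wrong drug. That is a ceiling under these assumptions; repeated errors in the same patient would raise it.

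**The case against.** The best defence is that the sentence fills a real gap. With supplies handed out visit by visit, a dispensing error normally produces mixed exposure, for which protocol 9.1 has no rule. Analysing such patients as randomised is simple, fixed in the SAP and usually close to the drug mainly taken. Harm is also contained. Protocol 7.5 records treatment errors in the dosage administration record, SAP 2.7.1 lists all adverse events, and serious events are reported individually. All of this stands. It limits the defect to patients with no mixed exposure, but it does not remove it, because the wording does not require that any randomised drug was taken.

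Two stronger readings are tempting. A reader might infer that the exception also misplaces patients who mainly, but not only, took the other drug. The documents do not make that an error: analysis as randomised is a defensible convention for mixed exposure, and the protocol sets no competing one. A reader might also enumerate wrong-kit patterns over the four dispensing visits and conclude that majority-wrong exposure is common. Such a count assumes one kit per visit, which protocol 5.5.2 and 5.5.4 do not establish, and it treats one error and four errors as equally likely.

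The per-protocol mismatch carries little weight, since SAP 2.5.5 makes that analysis optional: "The primary analysis may be repeated for the PPS". Nor can it be said that no listing of the drug taken is planned, because the table shells are not available.

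**Conclusion.** Wrong as written; minor severity. Applied literally, the SAP sentence would place the safety and exposure data of a patient who took only the other arm's drug under a treatment not taken during the double-blind period. Protocol 9.1 would place that patient under the drug taken, and the departure is not visibly declared.

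The number affected cannot be established from the documents and is probably very small. Common-event comparisons would hardly move. A rare or serious event could change arm, by about 0.61 percentage points per misplaced patient with an event at 325 per arm. FAS efficacy is unaffected, because that set is as randomised in both documents.

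The conclusion rests on the literal scope of the sentence and on the readable part of SAP Section 4.

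**What to change.** Limit the dispensing-error sentence to patients who also took at least one dose of their randomised treatment in the double-blind period. Those who took only the other arm's drug then follow protocol 9.1. The restriction to double-blind doses is needed because every patient takes placebo in the run-in.

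Deleting the sentence outright would leave mixed exposure without a rule. If the sponsor prefers a different convention, such as the treatment taken for most of the exposure with a tie rule, it should be fixed before unblinding.

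Declare any departure that is kept in SAP Section 4. List misdispensed patients with the drug taken, the dates and their events.

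The cost is one reworded sentence, one declaration, an actual-treatment flag and one listing. Arm counts in the Safety Set and FAS may differ by a few patients. The flag may take some effort: the kit label is kept in site source documents (protocol 5.5.2), and IRT records the kit assigned, which need not be the one handed over. Dosage administration records and label forms may have to be reconciled with the medication list.

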2.2.1 Subgroup of interest

Subgroup analyses will be performed for primary endpoint and secondary endpoints using the same model as for the primary analysis (mentioned in section 2.5.3) but with additional model terms for the subgroup (if not already included in the model) and subgroup-by-treatment interaction terms. The subgroup variables are listed below:

Key demographic subgroups:

- Age at entry into study (<18, ≥18 years)
- Sex (Male, Female)
- Race (Caucasian, Black, Asian, Other)
- Geographic region (Europe, Latin America, North America, China/AMAC)
The definition of geographic region will be same as the definition of region at the randomization

Disease related subgroups:

- Use or non-use of a second asthma controller medication
- Baseline FEV₁ (tertiles 1, tertiles 2, tertiles 3)
- Baseline %predicted FEV₁ (> 70%, ≤ 70%)

Subgroup analyses will be conducted on the FAS for exploratory purposes. Formal multiplicity adjusted testing on the subgroups will not be performed.

Subgroup analyses contributing key regulatory information will be provided for relevant country or region to meet regulatory requirements. Analyses required to fulfil health authority commitments or submission requirements for specific countries will be reported separately and outside of CSR.

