## Subgroups

The primary and secondary analyses will also be conducted by subgroup including for key demographic (e.g., age, sex, race, BMI, geographic region) and disease related subgroups (e.g. number of exacerbations in the previous year, use or non-use of a second asthma controller medication, baseline FEV1 tertiles, ACQ tertiles, XXXXXXXXXX).

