2.5.2 Secondary endpoints

The secondary endpoints are daytime asthma symptoms, total daily SABA use and AQLQ+12. Their definition and analysis is described in [Section 2.6](#).

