2.5.3 Statistical hypothesis, model, and method of analysis**2.5.3.1 Primary endpoint**

The primary objective of the study is to evaluate superiority of QAW039 150 mg once daily over placebo (with SoC asthma therapy as the background therapy) by testing the following null hypothesis (H₀) versus the alternative hypothesis (H_a):

H₀: There is no difference in the change from baseline in pre-dose FEV₁ (L) at week 12 post-baseline for the patients treated with QAW039 150 mg once daily compared with placebo ($\mu_1 - \mu_2 = 0$)

H_a: There is a difference in the change from baseline in pre-dose FEV₁ (L) at week 12 post-baseline for the patients treated with QAW039 150 mg once daily compared with placebo ($\mu_1 - \mu_2 \neq 0$).

where;

μ_1 = Mean change from baseline in pre-dose FEV₁ (L) at week 12 of QAW039 150 mg once daily treatment;

μ_2 = Mean change from baseline in pre-dose FEV₁ (L) at week 12 of Placebo treatment;

The primary efficacy variable will be analyzed on the FAS using an analysis of covariance (ANCOVA) model with factors for treatment group, randomization strata [age group (<18 vs. ≥18 years), use or non-use of a second asthma controller medication at study entry, and region], as well as the baseline daytime asthma symptom score, baseline total daily SABA use and baseline pre-dose FEV₁ as continuous linear covariates. The variables contributing to the randomization strata (i.e. age group (<18 vs. ≥18 years), use or non-use of a second asthma controller medication at study entry, and region) are included separately in the model.

The least squares mean (“adjusted mean”) change from baseline for each treatment group, the difference in the least squares (LS) mean changes between the two treatment groups (QAW039 150 mg – placebo), and the two-sided 95% confidence interval along with the p-value for the difference will be obtained and combined from the primary analysis model through the multiple imputation approach described in [Section 2.5.4](#).

The superiority of QAW039 150 mg once daily to placebo as add on to SoC asthma therapy is established if the two-sided p-value is less than 0.05 and the 95% confidence intervals lie entirely to the right of 0 L.

Summary statistics for the primary endpoint

Summaries of observed absolute values and change from baseline in pre-dose FEV₁ (L) by treatment group and visit will be presented.

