2.6.3 AQLQ+12

The 32 items in the AQLQ+12 are divided into 4 domain-specific scores and a total score as follows:

- Symptoms = Mean of Items 6, 8, 10, 12, 14, 16, 18, 20, 22, 24, 29, 30 (12 items)
- Activity limitation = Mean of Items 1, 2, 3, 4, 5, 11, 19, 25, 28, 31, 32 (11 items)
- Emotional function = Mean of Items 7, 13, 15, 21, 27 (5 items)
- Environmental Stimuli = Mean of Items 9, 17, 23, 26 (4 items)
- Overall Score = Mean of Items 1 to 32 (32 items)

Each item of the AQLQ+12 is equally weighted and scored along a 7-point scale, where 1 indicates maximal impairment and 7 indicates no impairment. Thus, higher scores indicate better asthma-related HRQOL (Health-Related Quality of Life). There is a mean score calculated for each of the four domains, as well as an overall quality-of-life score, which is the mean score of all 32 items. The resultant overall scores will be between 1 and 7.

The developer suggests no more than 10% of missing data. This means no more than 3 missing responses for the overall score and no more than 1 missing response per domain. For the

symptoms and activity domain scores, one missing value per domain is allowed. For the emotional function and environmental stimuli domain scores, no missing values are allowed. If these limits for missing questions are exceeded, the variable will be considered missing and will be imputed as described in [Section 2.6.4](#).

The minimal important difference (MID), defined as “the smallest difference in score which patients perceive as beneficial and would mandate, in the absence of troublesome side effects and excessive cost, a change in the patient’s management,” of 0.5 has been established for this questionnaire as clinically significant ([Juniper, et al 1994](#)).

The change from baseline in AQLQ+12 at week 12 will be analyzed using an ANCOVA model in a similar fashion as the primary efficacy variable, based on on-study data (including on-treatment and off-treatment data). The model will include factors for treatment group, age group (<18 vs. ≥18 years), use or non-use of a second asthma controller medication at study entry, and region, as well as the baseline daytime asthma symptom score, baseline total daily SABA use, baseline pre-dose FEV₁, and baseline AQLQ as continuous linear covariates.

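### SAP 2.2.1 points every subgroup analysis to the FEV1 model, so the AQLQ+12 subgroup estimates omit baseline AQLQ: a low-priority, cost-free correction

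*SAP*

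**What the plan says.** SAP 2.2.1 covers subgroup analyses of the "primary endpoint and secondary endpoints using the same model as for the primary analysis (mentioned in section 2.5.3"). It then states what is added: "but with additional model terms for the subgroup (if not already included in the model) and subgroup-by-treatment interaction terms". It describes these analyses as exploratory, on the FAS, without multiplicity-adjusted testing.

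Section 2.5.3 contains one model, in 2.5.3.1, for FEV1. Besides treatment, age group, second-controller use and region, it has "baseline daytime asthma symptom score, baseline total daily SABA use and baseline pre-dose FEV₁ as continuous linear covariates".

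SAP 2.5.2 places AQLQ+12 inside the subgroup rule: "The secondary endpoints are daytime asthma symptoms, total daily SABA use and AQLQ+12". The main AQLQ+12 ANCOVA in SAP 2.6.3 uses the same factors and the same three continuous covariates, with one more: "baseline pre-dose FEV₁, and baseline AQLQ as continuous linear covariates". The on-treatment MMRM and the responder logistic regression in 2.6.3 also include baseline AQLQ.

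Protocol section 9.4.4, under Subgroups, says: "The primary and secondary analyses will also be conducted by subgroup including for key demographic" and disease-related characteristics. SAP section 4, which lists departures from the protocol, moves some of the section 9.4.4 subgroup variables outside the study report. It declares no change to the subgroup model.

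**The concern.** The cross-reference in 2.2.1 is harmless for FEV1, daytime symptoms and SABA use, because each of those endpoints has its own baseline in the 2.5.3.1 model. AQLQ+12 is the one endpoint for which it fails. A programmer who follows the text leaves baseline AQLQ out; one who guesses at the intent puts it in. The two would produce different subgroup tables from the same plan.

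Subgroup estimates are read beside the overall estimate to judge consistency. Here the overall AQLQ+12 estimate would be adjusted for baseline AQLQ and the subgroup and interaction estimates would not. They would also be less precise than the data allow. The point concerns the analysis model fitted to each imputed dataset, not the imputation model.

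**Working it through.** **The plan's own figure.** The nearest stated figure is the 98% power for AQLQ+12 at local two-sided level 0.05 × 0.02 = 0.001 (SAP section 3: effect 0.5, SD 1, 325 per arm, 15% discontinuation). Diluting the effect by the discontinuation rate as an approximation to jump-to-reference gives 0.5 × 0.85 = 0.425. The standard error is √(2/325) = 0.0784. Then 0.425/0.0784 = 5.42, less the critical value 3.29, leaves 2.13, and power is 98.3%. The figure is reproduced. It belongs to the overall test and does not depend on the subgroup model.

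**Continuous covariates side by side.**

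| Model | Symptoms | SABA | FEV1 | AQLQ |
|---|---|---|---|---|
| SAP 2.5.3.1 (FEV1) | yes | yes | yes | no |
| SAP 2.6.1 (symptoms) | yes | yes | yes | no |
| SAP 2.6.2 (SABA) | yes | yes | yes | no |
| SAP 2.6.3 (AQLQ+12) | yes | yes | yes | yes |
| SAP 2.2.1 as written, AQLQ+12 | yes | yes | yes | no |

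Only for AQLQ+12 does the subgroup model differ from the endpoint's main model in its baseline covariates.

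**Loss of precision.** The documents give neither the correlation ρ between baseline and week-12 AQLQ nor the share R² of baseline AQLQ variance explained by the other covariates. I assume ρ from 0.4 to 0.7, R² from 0.2 to 0.5, equal variances at the two times (SD 1), and other covariates that act on the week-12 score only through baseline AQLQ.

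Write the week-12 score as y = ρb + e, with Var(e) = 1 − ρ². The change is y − b = −(1 − ρ)b + e. Residual variance is

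- with baseline AQLQ: 1 − ρ²
- without it: (1 − ρ)²(1 − R²) + 1 − ρ²

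The ratio is 1 + (1 − ρ)(1 − R²)/(1 + ρ), and its square root is the ratio of interval widths. The ratio does not depend on the SD.

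**Chance baseline imbalance.** With n per arm in a subgroup, imbalance shifts the unadjusted difference with SD (1 − ρ) × √(2/n) × √(1 − R²). I take n = 32, which is adolescents if they are 10% of 650 (an assumption), so √(2/32) = 0.25.

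| ρ | R² | Variance ratio | Interval width ratio | Information lost | Imbalance SD (points) |
|---|---|---|---|---|---|
| 0.4 | 0.20 | 1.34 | 1.16 | 26% | 0.134 |
| 0.5 | 0.35 | 1.22 | 1.10 | 18% | 0.101 |
| 0.7 | 0.50 | 1.09 | 1.04 | 8% | 0.053 |

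A wider grid (ρ 0.4 to 0.8, R² 0 to 0.5) gives standard errors 3 to 20% larger.

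**Are imbalance and wider intervals separate costs?** No. At ρ = 0.4, R² = 0.2, the imbalance variance is 0.134² = 0.018. The adjusted sampling variance is (1 − 0.16) × 2/32 = 0.0525. Their ratio, 0.018/0.0525 = 0.34, is exactly the 34% excess in the first row. The wider interval already contains the imbalance.

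**Bias.** In a simulation of 650 patients (4,000 runs per scenario, true effect 0.425, no true interaction), the mean treatment and interaction estimates were the same with and without baseline AQLQ, to within simulation error: about 0.425 and 0.00. With half the patients in the subgroup, the SD of the interaction estimate rose from 0.123 to 0.133 (ρ 0.6, R² 0.25) and from 0.136 to 0.157 (ρ 0.5, R² 0).

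**The case against.** The strongest reply is that this is a loose cross-reference, not an analysis choice. SAP section 1 says data will be analysed according to protocol section 9, and section 9.4.4 has each secondary analysis repeated by subgroup. SAP section 4 discusses those subgroups and declares no new model. SAP 2.6.3 itself describes the AQLQ+12 model as similar to the primary one and then adds baseline AQLQ, so the primary model may be meant throughout as a template. This is plausible, and it is a reason to correct the sentence. It does not make the sentence clear, because 2.2.1 names section 2.5.3 explicitly and lists the only terms to be added.

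The objections on harm stand. The subgroup analyses are exploratory. The size rests wholly on assumed values, and at the favourable end a 4% wider interval in an unpowered subgroup is negligible.

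Three stronger readings are tempting, and the documents support none of them:

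- A reader might infer that an unadjusted change score biases the subgroup effects through regression to the mean. In a randomised comparison it acts on both arms alike, and the simulation shows no bias.
- A reader might count chance imbalance as a harm on top of the wider intervals. It is the same variance, and only a fraction (1 − ρ) of any imbalance reaches the estimate.
- A reader might infer that the multiplicity-controlled AQLQ+12 result is at risk. That test uses the 2.6.3 model and is unaffected.

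**Conclusion.** The mismatch is real on the text. As written, AQLQ+12 subgroup and interaction estimates omit a covariate that every AQLQ+12 model in SAP 2.6.3 contains, and this departs without declaration from the protocol's rule that the secondary analyses themselves are run by subgroup. The estimates stay unbiased. The cost is confidence intervals about 4 to 16% wider (equivalent to losing 8 to 26% of the information in each subgroup), and subgroup estimates that are not on the same adjustment as the overall one. Within that variance, the SD of the shift from chance imbalance at 32 per arm is about 0.05 to 0.13 points, against the minimal important difference of 0.5 cited in SAP 2.6.3. All of these sizes depend on the assumed correlation, explained share, SD of 1 and, for the last, the subgroup size. No primary or secondary conclusion changes. This is a free improvement of low priority.

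**What to change.** In SAP 2.2.1, replace the reference to the primary model with a statement that each endpoint's subgroup analysis uses that endpoint's own main model: 2.5.3.1 for FEV1, 2.6.1 for daytime symptoms, 2.6.2 for SABA use, and 2.6.3 for AQLQ+12, including baseline AQLQ. The subgroup and subgroup-by-treatment terms are then added as now. If leaving out baseline AQLQ was intended, SAP section 4 should say so and give the reason.

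The cost is one sentence and one covariate in the AQLQ+12 subgroup programs. Baseline AQLQ is already collected (protocol Table 6-1) and defined (SAP Table 2-1). Sample size, alpha allocation and stated power do not change.
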